3.2. Outcome Measures

3.2.1. 3.2.1 Primary Outcome Measures

Safety

- Occurrence of vaccine-related SAEs from the time of the first study vaccination (M-001 or placebo) through approximately 6 months after the second M-001 study vaccination
- Occurrence of solicited injection site and systemic reactogenicity events on the day of each study vaccination through approximately 7 days after each M-001 vaccination
- Occurrence of clinical safety laboratory adverse events from the time of each study vaccination of M-001 through approximately 7 days after each M-001 vaccination

Immunogenicity

• Geometric Mean Percentage of T cell subsets expressing perforin, CD107a, IFN-γ, TNF-α, and IL2, alone or in combination, in CD4 and CD8 cells after stimulation with M-001 component peptides at baseline (Day 1) and 14 days after the second dose of M-001

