3.3. Study Definitions and Derived Variables

Geometric mean percentages (GMPs) are calculated as the product of the observed percentages raised to the 1/Nth root, where N is the number of observed values.

The baseline value for cellular and humoral immunity will be defined as the value obtained on Day 1 prior to M-001 vaccination.

M-001 antibody response after baseline will be summarized by GMTs and the proportion of subjects achieving seroconversion (defined as a minimum four-fold rise in post-vaccination ELISA antibody titer) at each time point, with corresponding 95% confidence intervals.

For individual subjects, fold rise will be calculated as the ratio of: $\frac{post-vaccination\ titer}{pre-vaccination\ titer}$, where pre-vaccination value is always the result obtained at Day 1, prior to the first M-001 dose.

Seroconversion for HAI and Neut assays is defined as either a pre-vaccination titer < 1:10 and a post-vaccination titer $\ge 1:40$, or a pre-vaccination titer $\ge 1:10$ and a minimum four-fold rise in post-vaccination titer.

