4.5.2. Immunogenicity Variables

Cellular immunogenicity data will be reported by the Baylor College of Medicine. These data will include the frequency of influenza-specific T cells as measured by fluorescence-based flow cytometric assays. The lab at Baylor will also report the percentage of influenza-specific T cells expressing discrete memory markers (CCR7, CD45RO, and CD57), the percentage of CD4 and CD8 T cells expressing perforin, CD107a, IFN- γ , TNF- α , and IL2, alone or in combination, the percentage of CD4+ T cell subsets expressing IL-4 or IL-17, T follicular helper (TFH) cells (CD4+, CXCR5+, PD-1+, IL-21+) , T follicular regulatory (Tfr) cells (CXCR5+, PD-1+, CD25+, CD127+) , and T regulatory cells (Tregs) (CD25+, Foxp3+)as measured by flow cytometry.

Individual HAI and Neut antibody results will be reported for the IIV4 vaccine strain by the central immunology laboratory at St Louis University. Assay results are reported as a reciprocal titer with values of $10*2^k$, where k=0, 1, 2, etc. The lower limit of detection for both the HAI and Neut assays is 1:10; values below the limit of detection are reported as '<10', and for analysis are imputed as one-half the limit of detection (10/2 = 5). For analysis, the geometric mean of repeated results for each sample will be computed and used as the response for all subsequent calculations. The variation arising from multiple measurements for an individual at a single time point will not be used in subsequent calculations. See Section 3.3 for definitions of derived variables for the analysis of HAI and Neut data.

Assays to determine serum levels of antibodies to M-001 will be performed by BiondVax.

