6.5. Missing Data

All attempts will be made to collect all data per protocol. As missing data are expected to be minimal, no imputation will be performed for missing values. Any data point that appears to be erroneous or inexplicable based on clinical judgement will be investigated as a possible outlier. If data points are identified as outliers, sensitivity analyses will be performed to examine the impact of including or excluding the outliers. Any substantive differences in these analyses will be reported.

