8.1. Primary Immunogenicity Analysis

The primary immunogenicity objective is to determine whether priming with M-001 improves T cell responses. The cells are sorted via flow cytometry, and the percentages of CD4+ and CD8+ T cells expressing perforin, CD107a, IFN γ , TNF- α , IL-2, or any combination of these are calculated as the number of cells positive for these proteins divided by the total number of T cells counted in each sample. To compare the T cell responses between groups, the following Poisson regression model will be fit for each combination of proteins of interest:

$$log(E(Y|X)/Z)=\beta_0+\beta_1*X,$$

where Y is the number of cells expressing a given combination of proteins, X is an indicator variable for Group A, and Z (the offset) is the total number of T cells in each sample. Wald tests will be performed to evaluate whether there are differences in the expression of T cell subsets between the two study arms. As described in Section 6.8, adjustments for multiple comparisons are not planned.

GMPs of CD4+ and CD8+ T cells expressing each combination of proteins and the corresponding 95% bootstrap confidence intervals will also be presented for each study armTable 22Table 23Table 24Table 25. These will be presented in Table 22, Table 23, Table 24, and Table 25 and summarized visually in boxplots over time in Figure 2, Figure 3, Figure 4, and Figure 5.

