[Implementation Note: Do not include p-value column for Tables 28-31, and only include it for Day 36 for Tables 25-27. Include rows for any perforin, any CD107a, any IFN- γ , any TNF- α , and any IL2.]

- Table 23: Geometric Mean Percentage (GMP) of CD8+ T Cell Subsets Expressing Markers Alone or in Combination After M-001 Stimulation with 95% Confidence Intervals by Study Day and Study Arm, Per Protocol Population*
- Table 24: Geometric Mean Percentage (GMP) of CD4+ T Cell Subsets Expressing Markers Alone or in Combination After M-001 Stimulation with 95% Confidence Intervals by Study Day and Study Arm, Modified Intent-to-Treat Population*
- Table 25: Geometric Mean Percentage (GMP) Of CD8+ T Cell Subsets Expressing Markers Alone or in Combination After M-001 Stimulation with 95% Confidence Intervals by Study Day and Study Arm, Modified Intent-to-Treat Population*
- Table 26: Percentage of CD4+ T Cell Subsets Expressing Markers Alone or in Combination After Seasonal Influenza A Antigen Stimulation with 95% Confidence Intervals by Study Day and Study Arm, Per Protocol Population
- Table 27: Percentage of CD8+ T Cell Subsets Expressing Markers Alone or in Combination After Seasonal Influenza A Antigen Stimulation with 95% Confidence Intervals by Study Day and Study Arm, Per Protocol Population
- Table 28: Percentage of CD4+ T Cell Subsets Expressing Markers Alone or in Combination After Pandemic Influenza A Antigen Stimulation with 95% Confidence Intervals by Study Day and Study Arm, Per Protocol Population
- Table 29: Percentage of CD8+ T Cell Subsets Expressing Markers Alone or in Combination After Pandemic Influenza A Antigen Stimulation with 95% Confidence Intervals by Study Day and Study Arm, Per Protocol Population

^{*}Wald test from Poisson regression used to compare groups.

^{95%} CIs calculated via 10,000 bootstrap samples.

Table 30: Summaries of Hemagglutination Inhibition Antibody Against A/Michigan/45/2015 X-275 (H1N1) by Study Day and Study Arm, Per Protocol Population

	Group A: 1 mg M-001 (N=X)	Group B: Placebo (N=X)
Day 1		
n	x	X
GMT (95% CI)	xxx.x(xxx.x,xxx.x)	xxx.x(xxx.x,xxx.x)
Titer ≥ 1:40 - %(95% CI)	x.x (x.x, x.x)	x.x (x.x, x.x)
Day 22		
n	x	X
GMT (95% CI)	xxx.x(xxx.x,xxx.x)	xxx.x(xxx.x,xxx.x)
Seroconversion - %(95% CI)	x.x (x.x, x.x)	x.x (x.x, x.x)
Titer ≥ 1:40 - %(95% CI)	x.x (x.x, x.x)	x.x(x.x, x.x)
Day 43		
n	x	X
GMT (95% CI)	xxx.x(xxx.x,xxx.x)	xxx.x(xxx.x,xxx.x)
Seroconversion - %(95% CI)	x.x (x.x, x.x)	x.x(x.x, x.x)

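### SAP 3.3 has no rule for zero percentages, so one subject with no positive cells sets that arm's geometric mean percentage to exactly 0 in that row of Tables 22–25

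*SAP*

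**What the plan says.** SAP 3.2.1 names the primary immunogenicity outcome measure as the "Geometric Mean Percentage of T cell subsets expressing perforin, CD107a" and the other markers, alone or in combination, after stimulation with M-001 peptides. SAP 3.3 defines the GMP as "calculated as the product of the observed percentages raised to the 1/Nth root", with N the number of observed values. SAP 8.1 defines each subject's percentage as "the number of cells positive for these proteins divided by the total number of T cells counted in each sample".

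For the interval, SAP 8.1 says that "the corresponding 95% bootstrap confidence intervals will also be presented" for each arm, and the Table 22 notes add "CIs calculated via 10,000 bootstrap samples". Neither place says whether the interval is percentile, basic or another type.

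The nearest rules do not cover a zero percentage:

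- SAP 4.5.2 has a floor for HAI and Neut titers only; values below 10 "for analysis are imputed as one-half the limit of detection (10/2 = 5").
- SAP 6.5 says "no imputation will be performed for missing values" and then deals with outliers. A measured 0% is not a missing value.
- The note under Listing 18 leaves zero percentages out of that listing. It shows that zeros were foreseen, but it does not govern the GMP.
- SAP 6.1, 8.1 and 12, the mock-up notes for Tables 22–25, and Protocol 11.5.4 and 11.5.5 are silent.

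**The concern.** A geometric mean is usable only when every value is above zero. Table 22 lists each of the 31 marker-positive combinations (2^5 − 1) of five markers, separately for CD4 (and Table 23 for CD8), so some rows may be rare subsets in which a subject has no positive cells.

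Followed literally, the plan would report a GMP of 0 for an arm in which all but one subject responded. Tables 22–25 give no other per-arm estimate, so the row would carry no information about size. It could stand beside a perfectly computable Wald p-value. The hypothesis in Protocol 11.1 is stated on the log of the GMP, which is undefined at 0.

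A GMP of 0 would be noticed, and the SAP Preface allows a justified deviation. But if it is first noticed in the unblinded tables, the rule is chosen with the results by arm in view, and in rows with many zeros the choice of rule changes the answer.

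**Working it through.** The plan states no figure to reproduce here, so the check applies its own formula.

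**Inputs from the documents.** 60 per arm, or 54 after 10% dropout (SAP Table 5); 57 = 60 × 0.95 under the 5% exclusion in SAP 5; log10 SDs of 0.25, 0.50 and 0.75 (SAP Table 5); 10,000 bootstrap samples. **Assumed, because the documents give no cell counts:** the median number of positive cells per sample and, where a percentage is needed, 50,000 T cells per sample.

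**1. Point estimate.** GMP = (x₁ × … × x_N)^(1/N). If any x = 0, the product is 0 and GMP = 0. The phrase in SAP 3.3 is loosely worded (Nth root or power 1/N is meant), but a zero factor gives 0 either way. No assumption is needed.

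**2. Bootstrap interval.** With k zeros among n subjects, the share of resamples containing a zero, and so having GMP = 0, is 1 − (1 − k/n)^n.

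| n | k = 1 | k = 2 | k = 3 | k = 4 |
|---|---|---|---|---|
| 54 | 63.56% | 86.97% | 95.43% | 98.43% |
| 57 | 63.54% | 86.94% | 95.41% | 98.42% |
| 60 | 63.52% | 86.92% | 95.39% | 98.41% |

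The 2.5th percentile is 0 once the share exceeds 2.5%, so from one zero. The 97.5th percentile is 0 once it exceeds 97.5%, so from four. A basic interval is (2 × GMP − upper percentile, 2 × GMP − lower percentile); with GMP = 0 and lower percentile 0 this is (−upper percentile, 0), a negative lower limit for a percentage.

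Demonstration: 57 log-normal percentages, median 0.05%, log10 SD 0.50, the lowest k set to 0, 10,000 resamples.

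| k | GMP | Percentile CI | Basic CI |
|---|---|---|---|
| 0 | 0.050 | (0.037, 0.067) | – |
| 1 | 0 | (0, 0.065) | (−0.065, 0) |
| 2 | 0 | (0, 0.062) | (−0.062, 0) |
| 3 | 0 | (0, 0.057) | (−0.057, 0) |
| 4 | 0 | (0, 0) | (0, 0) |

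**3. How often zeros occur.** For Poisson counts around a log-normal subject mean, P(zero for one subject) = E[exp(−median × 10^(SD × Z))], Z standard normal. Arm probabilities follow from the binomial with n = 57. Cells show SD 0.25 / 0.50 / 0.75.

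| Median positive cells | At least one zero | Four or more zeros |
|---|---|---|
| 5 | 83% / 99.5% / >99.9% | 9% / 76% / 98% |
| 10 | 20% / 86% / 99% | <0.1% / 13% / 71% |
| 20 | 1% / 44% / 91% | 0% / 0.3% / 21% |
| 50 | 0% / 8% / 55% | under 1% |
| 100 | 0% / 1% / 26% | under 1% |
| 200 | 0% / 0.2% / 9% | under 1% |

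With no between-subject variation at all, 1 − (1 − e^(−m))^60 gives 95%, 33%, 5% and 0.3% at a common mean m of 3, 5, 7 and 10 cells.

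**4. Does the rule matter once chosen?** In one simulated arm (60 subjects, median about 0.02%, log10 SD 0.75) with ten zeros, dropping them gives 0.0167; replacing them by 0.005, 0.001 or 0.0001 (%) gives 0.0137, 0.0105 or 0.0071. The extremes differ by 0.0167/0.0071 ≈ 2.4-fold. With one zero, the same four choices range only from 0.0182 to 0.0167.

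**5. Figure 2.** Its note selects the five combinations with the highest GMP without naming an arm or day. If the GMP used contains a zero, a more frequent combination can lose its place. With equal SDs and independent rows, the chance that a 40-cell combination has a zero while a 20-cell one has none is 0.04% / 7% / 6%. This is a secondary effect.

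**The case against.** The strongest reply is about weight. The between-arm comparison is the Poisson model, which accepts zero counts; the GMPs accompany it, and SAP 6.8 declares the primary immunogenicity analyses non-confirmatory. That is correct and limits the damage to the estimate and its interval. But that estimate is the named primary outcome measure.

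Second, no affected row can be shown from the documents. This stands too. The probabilities run from 0% to over 99.9% with the assumed median, and the Table 5 SDs come from a power calculation for IFN-γ, not for rare combinations. If those SDs are read as already including counting noise, the chance of at least one zero at SD 0.25 falls from 83% to 60% at 5 cells and from 20% to 12% at 10; at larger SDs the effect is small.

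Third, zeros can be counted on pooled data without treatment codes, and SAP 12 shows that the analysis was already revised once the data format was known. So an unblinded choice is possible, not inevitable. That supports writing the rule down while it can still be made blind.

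Fourth, the mock-up prints GMPs to one decimal, so small values might show as 0.0 anyway. This does not hold: the mock-up entries are placeholders, and SAP 10 reports summary statistics to one decimal more than the original data.

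Last, dropping zeros by analogy with Listing 18 would avoid the problem, but it is not stated for the GMP, contradicts N as the number of observed values, and biases the GMP upward.

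**Conclusion.** The concern holds and should be fixed. That one zero gives an arm GMP of exactly 0 under SAP 3.3 is certain. The failure of the percentile interval (lower limit 0 from one zero, (0, 0) from four) is equally certain for 54 to 60 per arm if that interval type is used.

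The number of affected rows is not known; it depends on cell counts that the documents do not give. Exposure is greatest for rare multi-marker combinations and least for the five rows for any expression of a single marker, since each of these is 0 for a subject only when all 16 combinations containing that marker are 0. The Poisson test can be computed with zeros; whether it is adequate is a separate matter, not judged here.

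**What to change.** In SAP 3.3, state one zero rule for the T cell GMPs in Tables 22–25, applied identically in both arms and at all visits, for example 100 × (count + 0.5)/(T cells counted + 1). For the any-marker rows, sum the counts before adding 0.5. Apply the same rule, with their own denominators, to the other cell-subset GMPs: Tables 26–29, and the tables from Table 38 onward, which include "the percentage of influenza-specific T cells expressing discrete memory markers (CCR7, CD45RO, and CD57"). Add the number of zeros per row and arm, name the bootstrap interval type, and pre-specify one sensitivity run with a different rule, such as 0.1 in place of 0.5, or replacing zeros only, as SAP 4.5.2 does for titers.

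The cost is a few sentences, one table column and one rerun; the counts are already needed for the Poisson model.

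The downside is that no rule is best throughout. In simulated arms of 57 (Poisson counts, 50,000 T cells assumed), the median GMP relative to the true median was:

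| Setting | Add 0.5 to all | Add 0.1 to all | Zeros only to 0.5 |
|---|---|---|---|
| 5 cells, SD 0.75 (about 9 zeros) | 1.14 | 0.83 | 1.03 |
| 10 cells, SD 0.50 (about 2 zeros) | 1.01 | 0.90–0.91 | 0.94 |

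Adding a constant to all counts also shifts rows without zeros slightly, and rows with many zeros must be read together with their zero counts. Fixing the rule in advance matters more than which constant is chosen.

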4. STUDY DESIGN

This is a Phase II randomized, double-blind, placebo-controlled trial in 120 males and non-pregnant females, 18 to 49 years old, inclusive, who are in good health and meet all eligibility criteria. This clinical trial is designed to assess the safety, reactogenicity, and immunogenicity of two priming doses of M-001 followed by administration of IIV4.

Subjects will be assigned randomly to 1 of 2 treatment arms (60 subjects per treatment arm) to receive two doses of the M-001 vaccine or placebo (saline) followed by a single dose of IIV4 (see Table 1). Group A will receive two doses of M-001, each containing 1 mg of M-001, on Days 1 and 22 followed by a single dose of IIV4 on approximately Day 172 (window for this visit ranges from Day 142 to Day 202). Group B will receive saline placebo on both Days 1 and 22, followed by a single dose of IIV4 approximately on Day 172.

Reactogenicity will be measured by the occurrence of solicited injection site and systemic reactions from the time of each study vaccination with M-001 (or placebo) through 7 days after the vaccination (inclusive of vaccination day). Unsolicited AEs will be collected from the time of each M-001 (or placebo) vaccination through approximately 21 days after each study vaccination. SAEs will be collected from the time of the first study vaccination through approximately 6 months after the second M-001 (or placebo) study vaccination. Clinical laboratory evaluations for safety will be performed on venous blood collected approximately 8 days after each M-001 (or placebo) vaccination (Days 9 and 30).

Immunogenicity testing will include performing HAI and Neut antibody assays on serum obtained immediately at baseline (Day 1) and on serum collected on Days 43, 172 and 200. ELISA antibody responses to the M-001 vaccine will be assessed on serum collected at baseline (Day 1) and on Days 22, 43, 78, 172 and 200. Cell-mediated immune responses to influenza antigens, including epitopes represented in the M-001 vaccine, and seasonal and candidate pandemic influenza viruses, will be assessed at baseline (Day 1), 14 days after each vaccination (Days 15, 36, and 186), approximately 21 days (Day 43) and approximately 56 days (Day 78) following receipt of the second M-001 (or placebo) dose, and immediately prior to and approximately 28 days after the IIV4 dose (Days 172 and 200).

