11.5.3. Humoral Immunogenicity Data

Summaries and analysis of immunogenicity data will be presented for the ITT and PP populations; the PP population will be considered the primary analysis.

Immune responses in terms of strain-specific (IIV4 strains) HAI and Neut antibody titers will be summarized by treatment arm at each time point. Analyses at all time points will include proportion of subjects with titers ≥ 40 and geometric mean titers (GMTs). Additionally the proportion of subjects achieving seroconversion from Day 172 to Day 200 (defined as either a pre-vaccination titer < 10 and a post-vaccination titer ≥ 40 or a pre-vaccination titer ≥ 10 and a minimum four-fold rise in post-vaccination antibody titer) will be presented. All summaries will include the corresponding 95% confidence intervals.

The proportion of subjects with seroconversion from Day 172 to 200 will be compared to evaluate the effect of M-001 priming using a two-sided Likelihood Ratio Test.

M-001 antibody response will be summarized by GMTs the proportion of subjects achieving seroconversion (defined as a minimum four-fold rise in post-vaccination ELISA antibody titer) at each time point, with corresponding 95% confidence intervals.

The correlation between HAI, Neut, and M-001 antibody titers will be evaluated. Plots such as reverse cumulative distributions or longitudinal presentations of GMTs will be presented for each assay.

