3.2.2. Secondary Outcome Measures

Safety

- Occurrence of all SAEs, from the time of receiving the first M-001 or placebo study vaccination through the end of the study
- Occurrence of all unsolicited non-serious AEs from the time of first study vaccination through 21 days after each M-001 vaccination

Immunogenicity

- For HAI and Neuts, the percentage of subjects achieving seroconversion (defined as either a prevaccination titer <10 and a post-vaccination titer ≥40 or a pre-vaccination titer ≥10 and a minimum four-fold rise in post-vaccination antibody titer) to IIV4 vaccine viruses from Day 172 to Day 200
- For HAI and Neuts, the percentage of subjects with an antibody titer of 40 or greater and geometric mean titers (GMTs) vs. IIV4 vaccine viruses on Days 1, 43, 172 and 200

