8.2. Secondary Immunogenicity Analyses

Humoral immune responses in terms of strain-specific IIV4 HAI and Neut antibody titers will be summarized by study arm at each time point. Descriptive summary statistics will be provided for all assays and time points including number of subjects with non-missing results, number and percentage of subjects with titers ≥1:40, number and proportion of subjects achieving seroconversion, and GMTs along with corresponding 95% CIs. Clopper-Pearson exact confidence intervals will be presented for proportion endpoints. Summaries of humoral immunogenicity endpoints are presented in Table 30, Table 31, Table 32, Table 33, Table 34, Table 35, Table 36, and Table 37.

HAI and Neut seroconversion by Day 172 or Day 200, the percentage of subjects with titer ≥40, and GMT's against the 2018-2019 IIV4 vaccine strain on Days 1, 43, 182, and 200 will be summarized as described above.

The reverse cumulative distributions of HAI and Neut assays against each strain will be displayed in Figure 10, Figure 11, Figure 12, Figure 13, Figure 14, Figure 15, Figure 16, and Figure 17. The Spearman correlation between HAI, Neut, and M-001 antibody titers will be calculated at each time point over all groups. The correlation will be depicted in scatter plots beginning at Figure 18 and continuing through Figure 29.

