12. SUMMARY OF CHANGES IN THE CONDUCT OF THE STUDY OR PLANNED ANALYSES

After the data format for the primary analysis was confirmed, the planned analysis was changed from what is described in the protocol. Instead of utilizing a normal approximation, a Poisson regression model will be fit to test for differences between study arms, as described in Section 8.1.

Additionally, the modified Intent-to-Treat population will only be used as a sensitivity analysis for the primary objective. Originally it was also planned for secondary and exploratory objectives involving antibody responses, but these will not be done in the interest of conciseness.

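### The SAP gives two reference days for the secondary HAI/Neut seroconversion endpoint (Day 172 in 3.2.2, Day 1 in 3.3) and drops the protocol's between-arm test of that endpoint without declaring it

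*SAP*

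**What the plan says.** **Endpoint.** Protocol 3.2.2, protocol 11.5.3 and SAP 3.2.2 agree that HAI/Neut seroconversion is measured from the pre-IIV4 sample to four weeks later: "to IIV4 vaccine viruses from Day 172 to Day 200".

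**Derivation.** SAP 3.3 fixes the "baseline value for cellular and humoral immunity will be defined as the value obtained on Day 1 prior to M-001 vaccination". For fold rise it adds that the "pre-vaccination value is always the result obtained at Day 1, prior to the first M-001 dose". The next paragraph defines HAI/Neut seroconversion through the pre-vaccination titre and a four-fold rise, and names no other day. SAP 4.5.2 sends the reader to 3.3 for HAI and Neut derived variables.

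**Analysis.** SAP 8.2 restates the endpoint as "HAI and Neut seroconversion by Day 172 or Day 200" and lists titre summaries against the "IIV4 vaccine strain on Days 1, 43, 182, and 200 will be summarized". Day 182 is not a scheduled study day. The Table 30 shell, shared by Tables 31-37, has seroconversion rows at Days 22, 43, 172 and 200, and states no reference day. Protocol section 4 schedules these assays at Day 1 and "on serum collected on Days 43, 172 and 200", so Day 22 is not an HAI/Neut day.

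**Test.** Protocol 11.5.3 says the Day 172-200 proportions "will be compared to evaluate the effect of M-001 priming using a two-sided Likelihood Ratio Test". SAP 8.2 plans only summaries with confidence intervals, and the shell has no p-value column. SAP Section 12 records two changes. One is that "a Poisson regression model will be fit to test for differences between study arms" for the primary analysis. The other restricts the mITT population to the primary objective.

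**The concern.** The two references answer different questions. From Day 172 to Day 200 the endpoint isolates the antibody response to IIV4 in subjects who were or were not primed. From Day 1 to Day 200 it also takes in whatever happened to the titre over the preceding 171 days: waning, infection, or a direct effect of M-001. Only the first is the stated endpoint.

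The omitted test is the only between-arm humoral test that protocol 11.5.3 names, and the protocol gives its purpose as evaluating priming. The SAP's preface says that the document describes all planned analyses, so a reader would conclude that the test was dropped, with no record of when or why. If either point is settled after unblinding, it becomes a choice made with knowledge of the results.

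**Working it through.** **1. Text, side by side**

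| Place | Reference for HAI/Neut seroconversion |
|---|---|
| Protocol 3.2.2, 11.5.3 | Day 172 |
| SAP 3.2.2 | Day 172 |
| SAP 3.3 | Day 1, without exception |
| SAP 4.5.2 | Refers to 3.3 |
| SAP 8.2 | Seroconversion by Day 172 needs an earlier sample |
| SAP Tables 30-37 | Not stated; rows at Days 22, 43 and 172 need an earlier sample |

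No row in Tables 30-37 is labelled as Day 172 to Day 200.

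**2. The reference changes who counts.** The rule (protocol and SAP) is pre <10 and post ≥40, or pre ≥10 and post/pre ≥4. Titres below 10 are set to 5 (SAP 4.5.2).

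| Day 1 / 172 / 200 | Day 1 reference | Day 172 reference |
|---|---|---|
| 10 / 40 / 80 | 80/10 = 8: yes | 80/40 = 2: no |
| 5 / 20 / 40 | <10 to 40: yes | 40/20 = 2: no |
| 40 / 10 / 40 | 40/40 = 1: no | 40/10 = 4: yes |
| 20 / 5 / 40 | 40/20 = 2: no | <10 to 40: yes |

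**3. How often (illustration).** The plan states no rate or power for this endpoint, so there is no figure to reproduce. Assumed, in log2 titre:
- Day 1 ~ N(log2 40, SD 1.8)
- Day 172 = Day 1 − waning + N(0, s)
- Day 200 = Day 172 + N(2, SD 1.3)

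Titres are rounded down to 10×2^k. There are 1,000,000 simulated subjects per scenario.

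| Waning (log2) | Status differs, s = 0 / 0.5 / 1.0 | Rate, Day 172 reference | Rate, Day 1 reference |
|---|---|---|---|
| 0 | 0 / 8 / 15% | Equal to the Day 1 rate within 0.3 points | Equal to the Day 172 rate within 0.3 points |
| 0.5 | 11 / 12 / 16% | 55-56% | 45-46% |
| 1.0 | 21 / 20 / 19% | 51-52% | 32-35% |

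With waning 0.5 and s = 0.5, varying the Day 1 GMT over 20-80 and the rise over 1.5-2.5 log2 gives 8-15% discordant.

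**4. Effect on the arm comparison.** Waning that is equal in both arms lowers both rates alike. Now suppose M-001 itself raises the Day 172 titre by 0.5 log2, with no waning and the same IIV4 rise in both arms, so that there is no priming of the rise. The arm difference is 11-13 points with the Day 1 reference and about 2 points with Day 172.

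**5. What the omitted test could detect.** Likelihood ratio test, exact binomial enumeration, two-sided 0.05, chi-square cutoff 3.84. Arm difference in points needed for 80% power:

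| Control rate | 30% | 40% | 50% | 60% |
|---|---|---|---|---|
| n = 60 per arm | 24.9 | 25.0 | 24.5 | 22.6 |
| n = 54 per arm | 26.5 | 27.0 | 25.4 | 23.6 |

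Four strains × two assays give 8 tests. Unadjusted and independent, the chance of at least one p<0.05 under no effect is 1 − 0.95^8 = 34%. Positive correlation between the tests would lower it.

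**The case against.** **The text may be a slip with an obvious answer.** The rule that the reference is always Day 1 follows the ELISA paragraph. SAP 3.2.2 matches the protocol, so a programmer has a clear text to query against. The 8.2 sentence is visibly garbled (Day 182) and may be a mistyped version of the endpoint. The Day 200 row of Table 30 could hold the Day 172-200 result. All this is possible, and it is only likely, not certain, that Day 1 would be programmed. It does not remove the contradiction: the fold-rise rule is not limited to ELISA, SAP 4.5.2 applies 3.3 to HAI/Neut, and the shell names no reference.

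**The illustration is assumed throughout.** This stands. The 2-point figure for Day 172 needs the IIV4 rise to be independent of the pre-IIV4 titre. If the rise falls by 0.2, 0.4 or 0.6 log2 per log2 of pre-titre (also assumptions; s = 0.5), the Day 172 arm difference becomes about −0.4, −3 or −5 points and the Day 1 difference about 10, 8 or 5. So Day 172 is not immune to a direct effect; the two references simply disagree. The simulation also ignores the averaging of replicate titres in SAP 4.5.2. With duplicates and an assumed within-sample SD of 0.3 log2, discordance with no waning and s = 0 is about 6% instead of 0%.

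**It is one secondary endpoint.** It has no stated hypothesis or power calculation. GMTs and the proportions with titre ≥40 are reported by arm, and every titre is listed, so either version can be recomputed. No primary or safety conclusion changes. This limits the damage. It does not justify two definitions of a stated endpoint or an unrecorded removal of a planned test.

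**Conclusion.** Both parts hold on the documents' own text, with high confidence. Following SAP 3.3 literally produces a different endpoint from the one in protocol 3.2.2 and SAP 3.2.2. The likelihood ratio test is absent from the SAP and its removal is undeclared. The no-adjustment statement in SAP 6.8 concerns the primary objective and does not explain the omission.

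The size depends on how titres move between Day 1 and Day 172, on which the documents are silent. Under the assumptions above, about 0-21% of subjects would be classified differently. The overall rate would shift by almost nothing without waning, by roughly 10 points with 0.5 log2 waning, and by 16-21 points with 1 log2. A distortion of the arm comparison needs a change before IIV4 that differs by arm. The test itself would have 80% power only for differences of about 23-25 points at 60 per arm, so its loss matters more for adherence to the plan than for sensitivity. The correction must be made before the analysis is programmed and unblinded.

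**What to change.** 1. **SAP 3.3:** state that for IIV4 HAI/Neut seroconversion the pre-vaccination titre is the Visit 9 (Day 172) sample taken before IIV4. Keep Day 1 for ELISA and for any summary of the period before IIV4.
2. **SAP 8.2:** describe seroconversion as from Day 172 to Day 200, and change Day 182 to Day 172.
3. **Tables 30-37:** add a labelled Day 172-to-200 seroconversion row by arm, state the reference day in a footnote, and remove the Day 22 rows. If a Day 1-to-200 figure is wanted, label it as a separate whole-regimen summary.
4. **Test:** either restore the two-sided likelihood ratio test for each strain and assay (8 unadjusted tests, labelled non-confirmatory), or state and justify its removal in Section 12. If it is restored, reporting the arm difference with a 95% CI would be more informative than the p-value alone; this is a suggestion beyond the protocol.
5. **Separate minor correction:** the Table 44 footnote applies the HAI/Neut rule to ELISA. Replace it with the four-fold-rise definition in SAP 3.2.3 and 3.3.

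The cost is SAP wording and table shells. Day 172 and Day 200 sera are already scheduled for these assays in protocol section 4, so no new sample or assay is needed.
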